# Participant Description

#### A) Participant or Sample Description:

- **Study Duration:** From the date of ethical approval until December 31, 2022.
- Type of Participants (e.g., normal controls or patients with specific diseases): Please specify: Diagnosed with obstructive sleep apnea syndrome (OSA).
- Estimated Number of Participants or Samples: 105; Age range: 20–65 years.
- Are participants selected by gender? □ Yes: □ Male □ Female No
- If there is a possibility of pregnancy among participants, does the study include pregnancy testing? □ Yes No
- If participants are children or disabled individuals, please explain the need for such participants:
- Describe the relationship between the principal investigator and the participants: ☐ Teacher/Student Researcher/Participant ☐ Healthcare Provider/Patient ☐ Employer/Employee
  - □ Friend □ Other, please specify:
- Describe the recruitment method for participants: Participants will be recruited from the ENT and sleep clinics at Cheng Kung University Hospital. After diagnosis and evaluation, patients with obstructive sleep apnea syndrome who consent to weight loss, use of CPAP, waiting for anti-snoring appliance production, or undergoing sleep surgery will be approached by the principal investigator, co-investigators, and research team. They will be given detailed information about the research intervention, procedures, and risks, and will be asked to sign a consent form. This will be a controlled experiment.

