**Table 1. Detailed Sampling Description** 

MFT: Y/Surgery: Z/Control: O	Week 0	Week 6	Week 18
Basic Data Collection			
Age, Gender, and Volumetric	Y/Z/O	Y/Z/O	Y/Z/O
Parameters			
Confounding Variables			
Medical History Record	Y/Z/O	Y/Z/O	Y/Z/O
Medication Record	Y/Z/O	Y/Z/O	Y/Z/O
Craniofacial Abnormality	Y/Z/O	Y/Z/O	Y/Z/O
Examination Record			
Sleep Clinical Symptoms Record	Y/Z/O	Y/Z/O	Y/Z/O
CT	Y/Z/O		Y/Z/O
Sleep-related Assessments			
Polysomnography	Y/Z/O		Y/Z/O
Drug-induced sleep endoscopy	Y/Z/O		Y/Z/O
Mental state assessment			
HADS	Y/Z/O	Y/Z/O	Y/Z/O
Muscle function tests			
Tongue	Y/Z/O	Y/Z/O	Y/Z/O
Pharyngeal Lateral Wall Muscles	Y/Z/O	Y/Z/O	Y/Z/O
Masticatory Muscles	Y/Z/O	Y/Z/O	Y/Z/O
Others	Y/Z/O	Y/Z/O	Y/Z/O
Biomarker test	Y/Z/O	Y/Z/O	Y/Z/O

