#### **Experimental Procedures and Methods:**

#### (1) Assessment Process:

Experimental Procedures and Testing Items: The experimental steps primarily

follow standard clinical procedures, detailed as follows:

- i. Screening through the sleep clinic to determine if further sleep-related assessments are needed (current clinical procedures).
- ii. Establishing the diagnosis of obstructive sleep apnea syndrome through sleep examinations (current clinical procedures, requiring overnight sleep studies at a sleep center).
- iii. Participants agree to self-weight management, use CPAP, await the fabrication of an anti-snoring dental appliance, or undergo sleep surgery.
- iv. Recruiting clinical participants based on inclusion and exclusion criteria, providing comprehensive study information, and informing participants of their right to withdraw from the study at any time. Participants will complete the consent form and will be orally introduced to the study grouping method during the clinic visit. Participants will choose their group based on personal preference and officially enter the clinical research study.
- v. Using computed tomography (CT) and drug-induced sleep endoscope examination to understand the pre-surgical pharyngeal anatomy.
- vi. Performing tongue muscle function tests, recording the results to understand pre-intervention functional indicators (approximately half an hour).
- vii. Conducting biomarker tests to understand pre-intervention biomarker indicators.
- viii. As detailed in Table 1, measurement parameters include sleep-related assessments, mental state assessments, drug-induced sleep endoscope examination, CT scans, respiratory-related muscle function tests, and biomarker tests. Pre- and post-surgical measurements, as well as follow-up measurements, will be conducted and repeated.
- Assessment Location: NCKU Hospital Physical Therapy Center

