#### 一、受試者或樣本資料:

- 研究期間: 人體研究倫理審查通過日至 111 年 12 月 31 日
- 受試者型態(如:normal controls,或罹患特殊疾病之病患) 請說明:患有阻塞性睡眠呼吸中止症確立診斷
- 受試者或樣本之估計數量: 105 人; 年齡範圍: 20~65 歲
- 是否有依性別選擇受試者或樣本? □是: □男性 □女性■否
- 如受試者有懷孕之可能,此研究是否包括懷孕檢測?□是 ■否
- 如受試者為孩童或殘障人士,請說明需要此類受試者之原因:
- 請說明計畫主持人與受試者之關係?
- □老師/學生 ■研究者/受試者 □醫療人員/病人 □雇主/職員 □朋友 □其它,請說明:
- 請說明受試者招募方式?

本研究將從成大醫院經耳鼻喉科及睡眠門診收案,門診醫師經診斷評估後為阻塞性睡眠呼吸中止症個案,個案同意自行減重、使用 CPAP、等待止鼾牙套製作或進行睡眠外科手術,由計畫主持人、共/協同主持人及協同研究員親自向符合收案條件的病患說明研究介入方式、實驗流程與風險後,經個案同意簽訂參與計畫同意書。為對照實驗。二、研究之主要納入與排除條件:

(1) 收案條件: 年紀介於 20~65 歲,已用 PSG 睡眠檢查新診斷為輕度到重度純粹阻塞性睡眠呼吸中止症病人, 愛普渥斯嗜睡度量表 ≧10,且已同意自行減重、使用 CPAP、等待止鼾牙套製作或接受睡眠外科手術治療者。

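### Pregnancy is an exclusion, but the protocol declines pregnancy testing and states no objective check before CT and drug-induced sleep endoscopy at Weeks 0 and 18

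*Combined protocol and SAP*

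**What the plan says.** The Exclusion Criteria list pregnancy in both the English and the Chinese text, and neither says how it is established. Women are eligible: the answer under Participant or Sample Description is that there is no selection by sex ("Are participants selected by gender? □ Yes: □ Male □ Female No"). The same section sets the size and age range: "Estimated Number of Participants or Samples: 105; Age range: 20–65 years".

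That section then asks, for the case where participants might be pregnant, "does the study include pregnancy testing? □ Yes No". In the English text as read, only the empty box beside Yes can be seen. The Chinese form settles the answer, because the box beside No is filled: "此研究是否包括懷孕檢測?□是 ■否".

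Table 1 uses one code per group ("MFT: Y/Surgery: Z/Control: O"). Its endoscopy row reads "Drug-induced sleep endoscopy Y/Z/O Y/Z/O", the two entries standing under Week 0 and Week 18, and the CT row has the same pattern. Figure 2 also lists both procedures at the start and at Week 18. In the Assessment Process, step iv applies the inclusion and exclusion criteria. Step v follows: "Using computed tomography (CT) and drug-induced sleep endoscope examination to understand the pre-surgical pharyngeal anatomy".

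Table 1 also contains "Medical History Record Y/Z/O Y/Z/O Y/Z/O", a history record in every group at Weeks 0, 6 and 18.

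**The concern.** The protocol regards pregnancy as important enough to exclude, then states that the study will not test for it, although every participant is scheduled for ionising radiation and drug-induced sedation twice. This is a recorded answer to a direct question, so it cannot be read as a detail left for later.

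The first stake is participant safety. A woman with an unrecognised pregnancy at entry, or one who conceives during the 18 weeks, could undergo the procedures without anyone knowing her status. The second is the data. Body composition, sleep measures and inflammatory markers are all collected, and a pregnancy during follow-up could plausibly shift them. The Statistical analysis section does not say whether measurements taken after a pregnancy begins are kept, set to missing or analysed separately.

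**Working it through.** No power, alpha or sample-size figure is involved, and the plan gives no figure of its own to reproduce. The check sets the provisions side by side and counts the scheduled procedures.

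**Inputs**
- Planned participants: 105, in three groups of 35 (Clinical Research; Participant or Sample Description).
- Visits with CT and endoscopy: 2, Weeks 0 and 18, all groups (Table 1).
- Pregnancy tests within the study: 0 (Participant or Sample Description; tick visible in the Chinese form).
- Point at which the exclusion is applied: recruitment, step iv, before the first CT and endoscopy in step v.

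**Count**
- Participants: 3 × 35 = 105.
- CT scans scheduled: 105 × 2 = 210, of which 105 are at Week 0 and 105 at Week 18.
- Drug-induced endoscopies scheduled: 105 × 2 = 210, split the same way.
- Procedures preceded by a study pregnancy test: 0 of 210 CT scans and 0 of 210 endoscopies.

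**What the stated provisions can detect**
1. *Pregnant at entry and aware of it.* Detectable at step iv, or through the Week 0 history record, if she is asked or volunteers it. The exclusion works here.
2. *Pregnant at entry and unaware.* No stated provision would find this before the Week 0 CT and endoscopy.
3. *Conceives after entry and is aware by Week 18.* The history record at Week 6 or 18 could capture it. Nothing links that record to the Week 18 procedures, and an entry criterion does not govern what happens during follow-up.
4. *Conceives after entry and is unaware at Week 18.* No stated provision would find this.

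Cases 2 and 4 are not covered, and case 3 is covered only by inference. Cases 3 and 4 also lack a data rule.

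**The case against.** The strongest reply is that answering No rules out a test within the study and nothing more. Eligibility is checked before the first CT and endoscopy. History is recorded in all groups at all three visits. The hospital may check pregnancy status before imaging, sedation or surgery as routine; the documents neither describe nor exclude this. The consent pages and some other pages were not available for review and could contain precautions.

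Much of this stands. A reader might infer that the exclusion cannot be enforced at either visit, and the documents do not support that. Self-report, the step iv criteria and the history record are a form of enforcement, though one limited to known pregnancy. At Week 18 an entry criterion is not being enforced at all; the gap there is the missing re-check and follow-up rule. If precautions do appear elsewhere, the No answer would still have to be squared with them.

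Two further inferences are tempting and should not be relied on:
- *Step order.* The biomarker blood test (step vii) is listed after CT and endoscopy (step v). The list does not say that the steps run in that order on the day, and no order is given for Week 18. It does not show that the blood sample would come too late.
- *Number of women.* Applying the protocol's population prevalences (4% in men, 2% in women), with equal numbers of each sex, gives 105 × 2/(4 + 2) = 35 women. These are general-population figures, whereas the cohort comes from one hospital's clinics and chooses its own treatment. No document gives the share who could become pregnant.

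It is also open whether both CT scans are research procedures. The Funding paragraph covers one CT and two endoscopies, while Table 1 schedules two of each. That is a separate inconsistency and does not alter the schedule used here.

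**Conclusion.** The concern holds in a limited form. The plan excludes pregnancy, admits women aged 20 to 65, declines testing, and schedules CT and drug-induced endoscopy twice in every group. As written, the exclusion reaches only known or reported pregnancy at entry. The available text contains no objective check at entry, no re-check before Week 18 and no data rule if pregnancy arises.

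The size that the documents support is 210 CT scans and 210 endoscopies scheduled without a study pregnancy test. That counts procedures in all participants, men included. It does not estimate exposed pregnancies, and the number of women affected cannot be derived. The conclusion rests on the Chinese form's tick applying to the English form too, and on the unseen pages not supplying a check. It has no bearing on the sample-size calculation, the significance level or power. It should be corrected, because it concerns participant safety and the change is simple.

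**What to change.** Reconcile the Exclusion Criteria, the pregnancy-testing answer and Table 1, in both languages:

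1. Change the testing answer to Yes.
2. Add a pregnancy-status row to Table 1 at Weeks 0 and 18, to be completed before CT and endoscopy, for women who could be pregnant. A urine test would serve, or a test on the blood already drawn at both visits. If the blood sample is used, state that it is taken and read before the procedures.
3. Add a sentence to the Statistical analysis section on how data are handled if a pregnancy arises after entry: which measurements are kept, which are treated as missing, and whether the participant remains in the between-group comparison.
4. Have the sponsor state what is done clinically after a positive result. This review does not propose that rule.

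The cost is a protocol amendment, a small testing expense for a subset of participants, and possibly a few missing Week 18 CT or endoscopy values. The tests fit within visits already planned. The documents give no unit costs, so the expense is not quantified here.

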#### B) Main Inclusion and Exclusion Criteria:

#### 1. Inclusion Criteria:

- o Age between 20 and 65 years.
- Diagnosed with mild to severe pure obstructive sleep apnea syndrome by PSG sleep study.
- o Epworth Sleepiness Scale score ≥10.
- Agreement to weight loss, use CPAP, wait for anti-snoring appliance production, or undergo sleep surgery.

#### 2. Exclusion Criteria:

- o Smoking, alcohol, or drug abuse within the past year.
- o Pregnancy.
- o Severe obstructive or restrictive pulmonary disease.
- o High-risk cardiovascular disease.
- History of central or peripheral neurological disorders that prevents participation in exercise prescriptions.
- Musculoskeletal or psychological disorders that prevent participation in

exercise prescriptions.

- o Other non-respiratory sleep disorders.
- o Coexisting central or mixed sleep apnea disorders.
- C) **Funding:** The study will be funded by internal grants covering one CT scan, two drug-induced sleep endoscopy examinations, and three blood sampling costs. Follow-up visits, outpatient consultations, and surgical costs will be borne by the patients.
- D) Methods for Ensuring Confidentiality of Participant or Sample Data:
  - **During the Study:** Use codes instead of participant names □ Other, please specify:
  - After the Study: Research results and published articles will not include identifiable participant information □ Other, please specify:

#### 對照臨床試驗

包含臨床研究以及生物標記研究兩個層面,其目的分述如下:(圖一)

#### ● 生物標記研究

本研究將檢測之生物標記包含 8-輕基-2  $^{\prime}$ -脫氧鳥苷(8-hydroxy-2-deoxyguanosine, 8-OHdG)、丙二醛(Malondialdehyde, MDA)、超氧化物歧化酶(superoxidase dismutase, SOD)、過氧化氫酶(catalase, CAT)、细胞核因子 $-\kappa$ B(nuclear factor kappa B, NF $-\kappa$ B)、腫瘤壞死因子 $-\alpha$ (tumor necrosis factor- $\alpha$ , TNF $-\alpha$ )、介白質 6(interleukin 6, IL-6)及基質金屬蛋白酶 9(Matrix metalloproteinases, MMP-9)。過去文獻顯示 OSA 產生的反覆性缺血及再灌流損傷,將造成活性氧化物(Reactive oxygen specie, ROS)、氧化壓力物質(如: 8-OHdG 及MDA)及發炎前驅物質(如: TNF $-\alpha$ 、IL-6) 過度產生,並損傷抗氧化能力。氧化壓力物質會造成 ROS 濃度上升,ROS 會活化 NF $-\kappa$ B 會刺激產生發炎前驅物質,並同時

調節 MMPs 的轉錄,TNF-α、IL-6 及 MMP9 的活化會造成內皮細胞失能,進而造成心血管疾病,已有研究發現阻塞性睡眠呼吸中止症患者血清中之 8-OHdG、MDA、NF-κB、TNF-α、IL-6 及 MMP-9 濃度有顯著性上升之情況,而抗氧化壓力物質(SOD 及 CAT)濃度有顯著性下降之情況,MDA、NF-κB 及 MMP-9 濃度與夜間氧氣飽和濃度低於 85%持續時間呈高度正相關性,而與平均血氧飽和濃度呈負相關性,另 MMP-9 又與血漿中IL-6 和 TNF-α 呈正相關性。希望藉由此研究了解瞭解 0SA 嚴重程度與心血管疾病危險因子之相關性,並探討手術及運動介入是否改善心血管疾病發生的危險因子。

目的(四)探討 OSA 嚴重程度,與心血管疾病危險因子之相關性

目的(五)探討運動介入是否改善心血管疾病發生的危險因子及精神狀態

實驗設備:圖(二)表(一)

A) 主要結果量測 (primary outcome)

- 睡眠相關檢查:
  - i. PSG(polysomnography)包含睡眠品質相關問卷量表: ESS(Epworth Sleepiness Scale), PSQI(Pittsburgh Sleep Quality Index)

- ii. 藥物誘導式睡眠內視鏡 Drug induced sleep endoscope examination (DISE)
- 電腦斷層掃描(Computed tomography, CT)
- B) 次要結果量測 (secondary outcome)
- 呼吸相關肌肉功能性檢測
  - i. 舌肌(Genioglossus): Iowa Oral Performance Instrument (Medical LLC, Carnation, WA)
- ii. 咀嚼相關肌群(Masticatory muscle function): dynamometer
- 精神狀態檢測:利用醫院焦慮與憂鬱量表(HADS)了解受試者最近1周之心情狀況 醫院焦慮憂鬱量表(Hospital Anxiety and Depression Scale, HADS),由 Zigmond 與 Snaith (1983) 針對醫院非精神疾病的門診病患,發展出合併焦慮與憂鬱疾病的身 體疾病患者之測量工具。此量表被翻譯成多國語言,並廣泛運用於臨床與研究上 (Quintana et al., 2003)。HADS 量表共有14題:包含7題測試焦慮(HAD-A)與7題 測試憂鬱(HAD-D)。每一題採四點計分法(0-3分),兩個量表分別計分,各量表總分21分,分數越高,表焦慮或憂鬱程度越高;總分0-7分表示正常,8-10分表示輕度,11-14分表示中度,15-21分表示嚴重;分量表總分0-7分表示無焦慮或憂鬱問題,8-10分表示有輕度焦慮或憂鬱情況,各分量表總分≥11分則為確定有焦慮與憂鬱之狀況(Zigmond & Snaith, 1983)。
- 分子生物學檢查:利用病人血清與細胞實驗分析生物標記(biomarker)包括:流 式細胞儀(FLOW)、 西方墨點法(western blot) 、酵素免疫分析法(ELASA)等。

對照組(減重、接受 CPAP 及等待止鼾牙套製作組)

計書開始初期量測

- 1. 隔夜式睡眠生理檢測
- 2. 電腦斷層掃描
- 3. 藥物誘導式睡眠內視 鏡檢查
- 4. 口腔舌咽肌肉功能檢測
- 抽血進行生物標記檢測
- 6. 精神狀態檢測

計畫開始第6週量測

[figure not shown]
- 1. 睡眠品質相關問卷量表
- 2. 口腔舌咽肌肉功能檢測
- 3. 抽血進行生物標記檢測
- 4. 精神狀態檢測

計畫開始第18週量測

- 1. 隔夜式睡眠生理檢測
- 2. 電腦斷層掃描
- 3. 藥物誘導式睡眠內視 鏡檢查
- 4. 口腔舌咽肌肉功能檢測
- 5. 抽血進行生物標記檢測
- 6. 精神狀態檢測

#### 12 週復健治療介入(運動組) 口腔顏面肌肉功能性訓練

- 1. 睡眠相關檢測
- 2. 電腦斷層掃描
- 3. 藥物誘導式睡眠 內視鏡檢查
- 4. 口腔舌咽肌肉功 能檢測
- 5. 生物標記檢測
- 6. 精神狀態檢測

手術組

運動組

第6週手術後量測

- 1. 睡眠品質相關問 卷量表
- 2. 口腔舌咽肌肉功 能檢測
- 3. 生物標記檢測
- 4. 精神狀態檢測

第18週追蹤量測

- 1. 睡眠相關檢測
- 2. 電腦斷層掃描
- 3. 藥物誘導式睡 眠內視鏡檢查
- 4. 口腔舌咽肌肉功 能檢測
- 5. 生物標記檢測
- 6. 精神狀態檢測

的田 Windo

#### 圖(二)採樣流程說明

#### 表(一)採樣細項說明

第 18 週	第0週	手術組 Z/對照組:0
		火集
Y/Z/0	Y/Z/0	、魔積描記參數
Y/Z/0	Y/Z/0	
Y/Z/0	Y/Z/0	
Y/Z/0	Y/Z/0	查記錄
Y/Z/0	Y/Z/0	狀記錄
Y/Z/0	Y/Z/0	棒描
		檢測
Y/Z/0	Y/Z/0	
Y/Z/0	Y/Z/0	的睡眠內視鏡檢查
		檢測
Y/Z/0	Y/Z/0	憂鬱量表
		机肉功能檢查
Y/Z/0	Y/Z/0	
Y/Z/0	Y/Z/0	肌等
Y/Z/0	Y/Z/0	群
Y/Z/0	Y/Z/0	
Y/Z/0	Y/Z/0	l&-ani
		檢測

#### 實驗流程及方法:

(1) 評估流程:

● 實驗流程及檢測項目:

實驗執行步驟多屬臨床處置標準流程,其細節如下說明:

- i. 透過睡眠門診篩檢是否需要進一步的睡眠相關檢測 (現行臨床處置流程)
- ii. 透過睡眠檢查確立阻塞性呼吸中止症候群診斷 (現行臨床處置流程,需要在睡眠中心進行過夜睡眠檢查)
- iii. 受試者同意自行減重、使用 CPAP 及等待止鼾牙套製作或進行睡眠外科手術
- iv. 依照收案以及排案條件徵收臨床受試者,提供完整詳細的研究說明,並告知受試 者有權利隨時終止參與計畫,完成受試者同意書填寫,此外也會在門診時口頭介 紹計畫分組方式,受試者將以自身意願決定進入之組別,正式進入臨床人體研究 計畫。
- V. 透過電腦斷層掃描及藥物誘導式睡眠內視鏡檢查,瞭解手術前口咽部解剖結構
- vi. 透過舌肌肌肉檢測,紀錄檢測結果,瞭解受試者介入前功能指標(約需半個小時 左右完成)
- vii. 透過生物標記檢測,瞭解受試者介入前生物標記指標
- viii. 如(表一)說明量測參數包含睡眠相關檢測、精神狀態檢測、藥物誘導式睡眠內 視鏡檢查、電腦斷層掃描、呼吸相關肌肉功能性檢測以及生物標記檢測,並依進 行手術前後量測以及追蹤量測等重複測試。
- 評估地點:成大醫院物理治療中心。
- (2) 研究程序及受試者應配合事項:蒐集受試者的基本資料(身體質量指數、體脂肪)等,再由物理治療師施行實驗相關之肌內功能性測試(肌力參數、姿勢評估)等等,治療計畫分別為手術及術後介入口腔舌咽肌內功能訓練12週,並進行手術前後量測以及追蹤量測等重複測試(圖二)。其量測項目包含睡眠專科醫師進行藥物誘導式的睡眠內視鏡檢查及電腦斷層掃描,睡眠專科技師進行睡眠檢查,專業物理治療師進行舌肌肌內功能檢查,以及專業護理人員血液採集,分別在第0週、計畫開始後或術後第6週和計畫開始後或術後第18週採血,一次採血20c.c,總共採血3次。

#### 預期結果:

故此,針對阻塞性睡眠呼吸中止症候群,本研究所提出的侵入性上呼吸道手術及非侵入性復健訓練,依照該族群病理發展機轉及其常發生的上呼吸道癱陷位置進行侵入性上呼吸道手術,並於術後介入咽部擴張肌的肌肉再教育之運動治療,預期可以改善睡眠 OSA 的臨床症狀,目前睡眠門診乃由診間專科護士進行相關居家介入之衛教,缺乏專業物理治療師執行運動訓練實務,希望藉由連續性的定期療程,追蹤並確認病患執行運動訓練的正確性以及有效性。此外,本實驗將透過生物標記的研究,進一步探討生物標記與臨床症狀的相關性,瞭解 OSA 嚴重程度與心血管疾病危險因子之相關性。故本研究以對照研究之實驗設計,從復健運動治療介入睡眠醫學,將是跨專業團隊合作發展的重大里程碑,同時也是未來臨床實務發展的重要指導守則。

#### 統計分析:

連續變數以均值和標準差(SD)表示,而分類變數以數量和百分比表示。使用 Kolmogorov-Smirnov 檢驗來分析變數的正態分布。由於分布不符合正態分布,對於連續數據和分類數據,分別使用 Kruskal - Wallis 檢驗和 Fisher 精確檢驗來比較研究組之間的基線特徵。此外,使用 Wilcoxon 符號秩檢驗比較人口特徵、問卷、睡眠參數和 CT 圖像數據的前後差異。使用帶有廣義估計方程(GEE)的線性回歸模型來估計(1)治療前後三組間差異的差異及其對應的 95%置信區間(CIs),以及(2)時間對肌肉力量和生物標誌物的多變量調整效果。工作相關矩陣定義為非結構化。P<0.05 被定義為統計學上顯著。所有統計分析均使用 SPSS 17.0 進行。

#### 受試者

描述

#### 一、受試者或樣本資料:

- 研究期間: 人體研究倫理審查通過日至 111 年 12 月 31 日
- 受試者型態(如:normal controls,或罹患特殊疾病之病患) 請說明:患有阻塞性睡眠呼吸中止症確立診斷
- 受試者或樣本之估計數量: 105 人; 年齡範圍: 20~65 歲
- 是否有依性別選擇受試者或樣本? □是: □男性 □女性■否
- 如受試者有懷孕之可能,此研究是否包括懷孕檢測?□是 ■否
- 如受試者為孩童或殘障人士,請說明需要此類受試者之原因:
- 請說明計畫主持人與受試者之關係?
- □老師/學生 ■研究者/受試者 □醫療人員/病人 □雇主/職員 □朋友 □其它,請說明:
- 請說明受試者招募方式?

本研究將從成大醫院經耳鼻喉科及睡眠門診收案,門診醫師經診斷評估後為阻塞性睡眠呼吸中止症個案,個案同意自行減重、使用 CPAP、等待止鼾牙套製作或進行睡眠外科手術,由計畫主持人、共/協同主持人及協同研究員親自向符合收案條件的病患說明研究介入方式、實驗流程與風險後,經個案同意簽訂參與計畫同意書。為對照實驗。二、研究之主要納入與排除條件:

(1) 收案條件: 年紀介於 20~65 歲,已用 PSG 睡眠檢查新診斷為輕度到重度純粹阻塞性睡眠呼吸中止症病人, 愛普渥斯嗜睡度量表 ≧10,且已同意自行減重、使用 CPAP、等待止鼾牙套製作或接受睡眠外科手術治療者。

#### (2) 排除條件:

- 一年內有抽菸、酒精和藥物濫用者
- 懷孕
- 嚴重阻塞性或限制性肺部疾病
- 運動高風險心血管疾病
- 中樞或周邊神經疾病病史導致無法執行運動處方
- 肌肉骨骼或心理障礙導致無法執行運動處方
- 其他非呼吸相關的睡眠疾患
- 合併中樞型或混合型睡眠呼吸中止症的睡眠疾患

